COMIRB Protocol

**COLORADO MULTIPLE INSTITUTIONAL REVIEW
BOARD
[name] [contact]
[contact]**

Protocol #: 18-1854

Project Title: Evaluation of pancreatic cystic lesions via EUS-guided fine needle aspiration with and without micro forceps biopsies: A randomized controlled study

Principal Investigator: [name]

Version Date: February 5, 2021

I. Hypothesis: Evaluation of pancreatic cystic lesions using endoscopic ultrasound with fine needle aspiration (EUS-FNA) of cyst fluid and microforceps biopsies (EUS-MFB) has greater diagnostic yield and equivalent safety profile compared to EUS with fine needle aspiration (EUS-FNA) alone.

Specific Aims: To prospectively compare the efficacy and safety of EUS evaluation of pancreatic cystic lesions with 1) EUS-FNA plus MFB versus 2) EUS-FNA alone, in a randomized controlled study.

II. Background and Significance:

Pancreatic cystic lesions (PCLs) are a common incidental finding in cross sectional imaging (up to 27% on CT scan and 41% on MRI¹) and pose a management challenge to physicians. According to society guidelines,²⁻⁴ PCLs with specific features should prompt additional workup with endoscopic ultrasound (EUS) for cyst characterization as well as cyst sampling. This can help determine if the cyst is mucinous or non-mucinous which has implications for its malignant potential. Cyst fluid has traditionally been sampled using EUS with fine needle aspiration (EUS-FNA) and sent for fluid analysis and cytology. However, despite use of a cyst fluid carcinoembryonic antigen (CEA) level cutoff⁵ of 192 ng/mL and cytology, accuracy of diagnosis for PCLs is poor. As the spectrum ranges from benign to high risk for neoplasm, precise diagnosis is critical.

More recently, the adjunctive use of the Moray® through the needle microforceps biopsy (EUS-MFB) has shown promise for diagnosis of PCLs.⁶ This technology utilizes a microforceps through a 19-gauge

needle to biopsy the cyst wall for histology, in addition to collecting cyst fluid for CEA level and cytology. Only a few small retrospective reports have been published regarding the use of MFB.

D. Innovation:

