Pancreatic cysts continue to pose a management dilemma for practicing clinicians, especially with the increased use of radiologic imaging modalities identifying incidental pancreatic cystic lesions with higher frequency. This leads to patient anxiety and increased costs due to radiologic surveillance and even surgery. The results of this study will hopefully help increase diagnostic yield by obtaining a histopathologic diagnosis of these PCLs, and potentially affect practice patterns of gastroenterologists and the endoscopic community, specifically those physicians who perform EUS in these patients. Furthermore, the results will help determine whether there is reason to continue this line of research to obtain a definite histologic tissue diagnosis of PCLs.

III. Preliminary Studies/Progress Report:

We recently published our retrospective series of 27 patients using EUS-MFB for evaluation of PCLs and reported technical success of 100% and obtained a pathological diagnosis in 24 of 27 cases (yield 88.9%) with MFB. In 7 patients (26%), microforceps biopsy results drastically changed the diagnosis, providing diagnoses otherwise not suggested by cytology or cyst fluid CEA levels. However, cytology provided a diagnosis of mucinous cyst in 4 cases (14.8%) not detected by microforceps biopsies. No adverse events were noted.

Other small retrospective studies have shown that cyst fluid analysis via FNA is comparable to MFB for distinguishing mucinous from non-mucinous cysts, but MFB is better at diagnosing the specific cyst subtype.^{8,9} However, prospective data on the use and safety of MFB for PCLs is lacking.

IV. Research Methods

The study will be performed at 3 participating sites:

- (1) University of Colorado Hospital-Anschutz Medical Campus (UCH-AMC), Aurora, CO (Primary site)
- (2) Mt. Sinai Medical Center, New York, NY
- (3) University of California, Irvine, CA.

The study will be conducted after obtaining approval from the Institutional Review Board at all sites.

A. Outcome Measure(s):

Primary Outcomes:

A. Compare the efficacy and safety of EUS-FNA plus MFB, with EUS-FNA alone for evaluation of PCLs

Definitions:

A. Efficacy will be defined as technical and clinical success in performing MFB during EUS evaluation of PCLs.

(1) Technical success will be defined as the ability to puncture the cyst with the FNA needle under EUS guidance, advance the micro forceps into the cyst to perform cyst biopsies and obtain a visible tissue fragment.

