(2) Clinical success will be defined as the ability to obtain a pathologic tissue diagnosis of the PCL with MFB. Based on prior experience, expected diagnoses include pseudocyst, serous cystadenoma, mucinous cyst (mucinous cystic neoplasm, intra-ductal papillary mucinous neoplasm), adenocarcinoma, and neuroendocrine tumor, to name a few.

B. Compare safety of EUS-FNA plus MFB with that of EUS-FNA by recording adverse events per published ASGE criteria (10).

Secondary Outcomes:

A. Technical ease in performing FNA and MFB:

(1) Ease of passage of FNA needle

(2) Ease of passage of Micro Forceps

(3) Ease of EUS visualization of Micro Forceps

Technical ease will be scored on a predetermined 5-point Likert scale (1 = best, 5 = worst)

B. Time taken for FNA and time for MFB

B. Description of Population to be Enrolled:

Inclusion criteria:

- Adult patients >18 years old
- Cysts > 20 mm in size deemed appropriate for FNA by the endoscopist, based on clinical presentation, radiologic imaging features, associated solid mass or nodules, and patient anxiety about the diagnosis

Exclusion criteria:

- Age <18 years
- Inability to provide informed consent
- Thrombocytopenia (Platelets < 50,000) or coagulopathy (INR > 1.8)

- Pregnancy
- Post-surgical anatomy where the cyst is not accessible for FNA
- EUS findings suggesting that cyst FNA would be unsafe (e.g. intervening blood vessels)
- EUS appearance suggesting FNA is not indicated (e.g. cyst smaller than prior radiologic imaging, cyst not seen, EUS suggestive of serous cystadenoma)

C. Study Design and Research Methods

Patients will be provided the necessary information regarding the study and consent will be obtained either in person and/or electronically through medical records depending on specific site IRB approval guidelines. Patients will be randomized to intervention 1) EUS-FNA plus MFB or 2) EUS-FNA alone

D. Description, Risks and Justification of Procedures and Data Collection Tools:

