Patients will be enrolled in this study when evaluated in GI clinics, hospital wards, and endoscopy suites. Consent for the study will be obtained either in person, by the interventional endoscopist who will be performing the procedure or by the research assistant/ study coordinator or electronically through medical records depending on specific site IRB approval guidelines. All UCH interventional endoscopists who perform EUS will participate in the study. All participating investigators are experienced interventional endoscopists proficient in EUS. Initial evaluation of patients will include collection of data on demographics, history, physical examination and pertinent radiologic, laboratory, and endoscopic data, and prior management/therapies. Details of previous endoscopic and surgical evaluation along with histopathology data will be documented, as needed for clinical care.

After obtaining informed consent, subjects will undergo EUS per clinical protocol. All procedure-related clinical decisions and interventions will be dictated by the performing physician as he or she sees fit. Once the pancreatic cystic lesion is seen and assessed by EUS, randomization will be performed after determination by the endoscopist and research coordinator that the patient meets inclusion criteria and does not have exclusion criteria.

A pancreatic cyst with high risk stigmata (presence of dilated main pancreatic duct > 10 mm, mural nodule or associated solid mass) would be referred for surgical resection based on patient's clinical status, irrespective of cyst fluid analysis/cyto/pathology. Cysts without high risk stigmata are followed with radiologic surveillance imaging in 1-3 years

Procedure description:

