Use of fine needle aspiration as well as micro forceps biopsy for pancreatic cysts is safe with low rates of adverse events. Therefore, the risk to the patient is minimal. Additionally, accurate diagnosis is critical, as pancreatic cysts range from benign to malignant. Thus, comparing two interventions to evaluate cystic lesions to determine the optimal modality for diagnosis is justified.

Data collection will be carried out by the study team under the direction of the principal investigator. A REDCap database will be used to store clinical data information for subjects who consent to participate. This will serve as a clinical data repository for subject data. Clinical data will be extracted by the investigators or PRA from medical chart review. Access to the REDCap database will be granted by the study team, sometimes in limited fashion (e.g. no access to identifiers), to research staff and to co-investigators when needed. The final responsibility for the completeness and accuracy of all study data will belong to the principal investigator.

The study team will reach out to the subject at two different points post procedure.
1) Up to 72 hours post-procedure to collect data on the first 24 hours and
2) At day 30 to collect data AE data from the previous 30 days. Adverse events will be recorded per published ASGE criteria (10). The PI will continuously review local AEs and a safety officer not directly participating in the endoscopic procedures will review adverse events every 6 months. The PI will review serious device related events within 48 hours of the lead site becoming aware of the event. No serious adverse events were seen in our initial study (7) and in the study by Basar et al (9). Potential adverse events after these procedures include bleeding, perforation, infection, pancreatitis, and sedation-related complications, to name a few. Based on prior experience (7, 9) we do not expect a high rate of adverse events. Hence, we do not anticipate the need for an interim analysis.

E. Potential Scientific Problems: N/A

F. Data Analysis Plan:

The primary outcome of the study is to compare the diagnostic yield of the efficacy and safety of EUS-FNA plus EUS-MFB, with EUS-FNA alone for evaluation of PCLs.

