Descriptive statistics will be used to summarize the data. Continuous variables will be expressed as mean \pm standard deviation and categorical variables will be mentioned in percentages. T-test for continuous variables and Fisher's exact test or chi-square test for categorical variables will be used as appropriate.

Sample size calculation was performed as follows: to power the study to detect a 20% difference in efficacy would require enrollment of 76 patients in each group. However, after accounting for screen failures, technical failures in performing FNA/MFB based on actual findings during EUS where FNA/MFB would not be possible, patient drop out and loss to follow-up, we estimate 25% more patients would need to be included i.e. 102 patients would be needed in each group to get 76 patients in each arm who would actually get FNA/MFB. Statistical

analysis will be independently performed by intention to treat analysis by the University of Colorado Center for Innovative Design and Analysis, not by the PI

G. Summarize Knowledge to be Gained:

Most of the current data on evaluation of PCLs emphasizes the limitations in cyst sampling techniques and technologies. We are still far from being able to accurately diagnose many of these lesions. We have recently published results showing the safety and efficacy of the microforceps biopsy in a retrospective cohort, and much of the other data on MFB comes from case reports and small retrospective case series. There has never been a head to head trial comparing these two interventions. Additionally, there is no “standard” intervention and approach to PCLs is largely influenced by practice patterns among physicians as well as equipment availability. This is a prospective randomized controlled study that will help answer the question on which approach lends itself to more technical success and higher diagnostic yield while monitoring safety profile.

H. References:

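### Safety is part of the primary outcome, but the plan describes no masking of those who collect, review or classify adverse events and does not say who assigns the ASGE grade

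*Combined protocol and SAP*

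**What the plan says.** **Safety is primary.** Section IV.A lists as the primary outcome "Compare the efficacy and safety of EUS-FNA plus MFB, with EUS-FNA alone for evaluation of PCLs". Section IV.F repeats it: "The primary outcome of the study is to compare the diagnostic yield of the efficacy and safety of EUS-FNA plus EUS-MFB". The hypothesis in Section I is that the combined procedure "has greater diagnostic yield and equivalent safety profile compared to EUS with fine needle aspiration (EUS-FNA) alone". Section IV.A measures safety by adverse events recorded under the published ASGE criteria.

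**Who handles the events (Section IV.D).**
- The study team collects the data under the PI's direction and contacts each patient twice, within 72 hours of the procedure and at day 30.
- On review: "The PI will continuously review local AEs and a safety officer not directly participating in the endoscopic procedures"; the sentence ends by saying that the officer "will review adverse events every 6 months".
- The PI also looks at serious device-related events within 48 hours of the lead site learning of them.
- Allocation takes place during the EUS examination, after the endoscopist and the research coordinator have confirmed eligibility.

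**Where independence is specified.** Section IV.F says that "analysis will be independently performed by intention to treat analysis by the University of Colorado Center for Innovative Design and Analysis, not by the PI". Nothing comparable is said about the step that produces the event list.

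**The concern.** Whether a borderline occurrence counts as an event, how severe it is and whether the procedure caused it can all involve judgement. If the person judging knows the arm, expectation can enter the count.

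The plan does state an expectation. Section IV.D describes both techniques as safe with few adverse events, and Section III reports the lead site's own series of 27 MFB patients with none. At that site, "All UCH interventional endoscopists who perform EUS will participate in the study".

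The effect could go either way. Confidence in MFB could lead to under-recording in that arm, which pushes the result towards the hypothesised similarity. Closer attention to the newer tool could create an apparent excess. Independent analysts cannot correct either one, because they start from a list that is already classified.

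**Working it through.** **1. The masking question, step by step**

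| Step | Who, per Section IV.D or IV.F | Masking stated? |
|---|---|---|
| Contact and data collection | Study team, directed by the PI | No |
| Assigning the ASGE grade | Not named | No |
| Continuous review | PI, local events | No |
| Serious device-related events | PI, within 48 hours | No; calling an event device related draws on knowing which device was used |
| Periodic review | Safety officer outside the procedures, every 6 months | No; no grading duty given |
| Statistical analysis | University centre, not the PI | Independent, but after classification |

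**2. The plan's own numbers.** The only sample-size figures are for efficacy: 76 per group, raised to 102 for a 25% loss. This reproduces: 76 / (1 − 0.25) = 101.3, rounded up to 102. The plan gives no expected adverse event rate, so everything below uses assumed rates or counts. Both denominators are shown, because 76 is the number expected to receive FNA/MFB and 102 is the number enrolled under intention to treat.

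**3. How few events there might be.** Expected events per arm = rate × n.
- 2%: 0.02 × 76 = 1.5; 0.02 × 102 = 2.0
- 5%: 0.05 × 76 = 3.8; 0.05 × 102 = 5.1
- 10%: 0.10 × 76 = 7.6; 0.10 × 102 = 10.2

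The earlier series does not settle the rate. With 0 events in 27, the upper two-sided 95% exact limit is 1 − 0.025^(1/27) = 12.8%.

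**4. What one classification is worth.** One event is 1/76 = 1.3 percentage points, or 1/102 = 1.0. Three events are 3/76 = 3.9 points, or 3/102 = 2.9.

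**5. Effect on the planned test.** Section IV.F names Fisher's exact test or chi-square. With 9 events in all, the expected count is 4.5 per arm, so Fisher's test (two-sided) is the natural choice.

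| Events, MFB arm vs FNA arm | p, 76 per arm | p, 102 per arm |
|---|---|---|
| 8 vs 1 | 0.034 | 0.035 |
| 7 vs 1 | 0.063 | 0.065 |
| 6 vs 0 | 0.028 | 0.029 |
| 5 vs 0 | 0.058 | 0.059 |

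In each pair, one event classified differently moves the result across 0.05.

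**6. Under-recording.** Suppose the true rates were 10% with MFB and 5% without, and half of the MFB-arm events were recorded. The observed difference would be 0.10 × 0.5 − 0.05 = 0. This shows the mechanism and is not a prediction.

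**The case against.** A reader might infer that the PI knows every allocation and decides which events count, or that every assessor knows the arm. The documents do not support that. They do not say that the PI is unmasked or performs the procedures, and they do not describe the safety officer's access to allocation. The PI is said to review events, and in the continuous review only local ones, in a three-site study. That the PI knows the arm is a plausible inference, since no masking is described and only the officer is set apart from the procedures, but it remains an inference. The supportable point is what the plan leaves unsaid.

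The plan also has real safeguards: the same two contacts in both arms, published criteria, and a reviewer outside the procedures. The complications that Section IV.D names include perforation and bleeding, which may leave less room for judgement than a mild symptom. How much discretion the ASGE criteria allow cannot be judged from these documents.

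The arithmetic is illustrative. Three events against none at 76 per arm would move the difference by 3.9 points but give Fisher p = 0.245, so not every small shift changes the test. The counts in the table that do cross 0.05 are chosen examples.

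Finally, the safety comparison has other weaknesses: equivalence is claimed without a margin, and the sample size rests on efficacy. At an assumed 5% versus 10%, exact power with 76 per arm is only 0.13. Masked grading does not repair that.

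All of this limits the strength of the point. It leaves the gap in place, because the same schedule and criteria do not stop knowledge of the arm from influencing how they are applied.

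**Conclusion.** The concern holds as a gap in how a primary endpoint is protected. No masking is described at collection, review or classification, no grader is named, and independence begins only at the analysis. Bias is possible, not shown, and its direction cannot be predicted.

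Its size depends on an event rate that the plan does not give. If events are few, as the plan expects, each one is worth 1.0 to 1.3 percentage points, and one reclassification can decide the test in cases such as 8 versus 1 against 7 versus 1. The conclusion assumes that some events leave room for judgement on occurrence, severity or relatedness. It does not assume that anyone has judged or would judge unfairly. The change is worth making because it is cheap and leaves the sample size and randomisation untouched.

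**What to change.** For the primary safety comparison only, amend Sections IV.D and IV.F as follows.

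- At each six-monthly review, the existing safety officer classifies every reported untoward event from all three sites under the cited ASGE criteria: event yes or no, severity, and relatedness to the procedure as a whole. Judging the whole procedure means that the officer does not need to know whether forceps were used.
- The officer works from short narratives with arm, forceps use and MFB result removed.
- The grading for that review is locked before any arm-level safety tally is shown.
- Both arms are asked the same fixed list of events at both contacts. The complications already named in Section IV.D are a natural start.
- Site and PI review for care and reporting, including device-related events, stays as it is.

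**Cost.** Protocol wording, brief narratives for what should be a small number of events, and slightly more officer and coordinator time. No new staff are needed. Masking will be partial: some narratives will reveal the arm, and the coordinator preparing them may know it. Sending the officer every reported untoward event, not a preselected list, limits the second problem but does not remove it.

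### One 25% allowance mixes losses before randomisation with technical failures that intention to treat counts as outcomes, and efficacy success is defined only through MFB, so the power of the planned comparison cannot be read from the plan

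*Combined protocol and SAP*

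**What the plan says.** Section IV.F (Data Analysis Plan) takes 76 per group as enough to detect a 20% difference in efficacy. It then adds an allowance: "we estimate 25% more patients would need to be included". The allowance covers screen failures, "technical failures in performing FNA/MFB based on actual findings during EUS where FNA/MFB would not be possible", drop-out and loss to follow-up, with no split by cause. The result is that "102 patients would be needed in each group to get 76 patients in each arm who would actually get FNA/MFB". The same paragraph says that "analysis will be independently performed by intention to treat analysis".

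Section IV.A gives the efficacy definition: "Efficacy will be defined as technical and clinical success in performing MFB during EUS evaluation of PCLs". Technical success requires the operator to puncture the cyst and "advance the micro forceps into the cyst to perform cyst biopsies and obtain a visible tissue fragment". For the clinical part, "Clinical success will be defined as the ability to obtain a pathologic tissue diagnosis of the PCL with MFB". No matching definition is given for FNA alone. The hypothesis (section I) and the opening of section IV.F instead make diagnostic yield the comparison.

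Section IV.D randomises after the EUS assessment and eligibility check, and before puncture. In both arms cyst fluid goes for CEA and cytology.

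**The concern.** Extra enrolment replaces patients who yield no data. It does not replace patients whose data are failures. Once a patient is randomised, a technical failure stays in the intention-to-treat denominator. If failures lower both arms' success rates by a fraction f, the true difference becomes 20 × (1 − f) points whatever the sample size. More patients add precision but do not bring the 20 points back.

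The plan's wording fits two accounts. Either the failures happen at or after puncture and belong in the assumed success rates, or they are cysts found unsuitable on EUS, which the exclusion criteria in section IV.B remove before randomisation. The second kind has no group, so it does not belong in a per-group figure of randomised patients. A reader therefore cannot tell whether 76 or 102 per arm will be randomised.

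The scoring needed to settle this is also missing. Applied literally, the MFB-based definition gives the control arm no way to succeed. Nor does the plan say how to count an MFB-arm patient whose biopsy failed but whose fluid gave a diagnosis. Section III shows this is a real category: cytology gave a mucinous diagnosis in 4 of 27 cases that MFB did not detect.

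**Working it through.** **The plan's own figures.** 76 / (1 − 0.25) = 101.3, rounded up to 102. So 102 is a 25% loss. Literally 25% more than 76 is 76 × 1.25 = 95.

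The 76 cannot be reproduced uniquely, because alpha, power and rates are not stated. One standard setting that reaches it is 63% v 83%, two-sided 5%, 80% power, p̄ = 0.73:

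n = [1.960·√(2·0.73·0.27) + 0.842·√(0.63·0.37 + 0.83·0.17)]² / 0.20² = (1.2306 + 0.5148)² / 0.04 = 76.2.

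**Inputs.**
- From the plan: 76 and 102 per group; a 20% difference, read as 20 points; MFB yield 24/27 = 88.9% and technical success 100% in the retrospective series (section III).
- Assumed: two-sided 5%, uncorrected chi-square, exact binomial power, and every patient's outcome known. Rates are 63% v 83%; 68.9% v 88.9% (the series yield less 20 points); and 16% v 36% as a low pair, for which the same formula gives 75. The technical failure rate after randomisation, f, is 5% or 10%.

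**Method.** Under a common yield endpoint:
- Failures in both arms: each rate is multiplied by (1 − f). For 63% v 83% this gives 59.85% v 78.85% (19 points) and 56.7% v 74.7% (18 points).
- Failures of MFB only, with fluid still diagnosed at the FNA rate: the MFB arm becomes 0.83(1 − f) + 0.63f, that is 82% and 81%.

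Power is the binomial probability, summed over all pairs of counts, that |z| ≥ 1.96, where z is the pooled two-proportion statistic.

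| FNA v MFB | Randomised per arm | No failures | Both arms 5% / 10% | MFB only, keeps FNA yield 5% / 10% |
|---|---|---|---|---|
| 63% v 83% | 76 | 80.4% | 72.5% / 65.4% | 75.6% / 70.3% |
| 63% v 83% | 102 | 90.5% | 84.5% / 77.7% | 86.9% / 82.6% |
| 68.9% v 88.9% | 76 | 87.4% | 78.3% / 69.3% | 82.9% / 77.7% |
| 68.9% v 88.9% | 102 | 94.8% | 88.9% / 81.8% | 92.0% / 88.3% |
| 16% v 36% | 76 | 81.5% | 78.7% / 75.8% | 77.8% / 73.7% |
| 16% v 36% | 102 | 91.1% | 89.2% / 86.9% | 88.5% / 85.2% |

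**Reading the table.** If 102 per arm are randomised and analysed, 5% failing in both arms leaves power above that of 76 undiluted patients for every pair. At 10% it falls below that mark for the two high pairs (77.7% against 80.4%; 81.8% against 87.4%) but not for the low pair. If only 76 are randomised, nothing offsets the failures.

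**The choice of test matters too.** Section IV.F allows "exact test or chi-square test for categorical variables will be used as appropriate". With Fisher's test, 63% v 83% and 102 per arm, power is 87.6%, 80.8% and 73.2% at 0%, 5% and 10% failing in both arms.

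**The case against.** The best defence is that the plan makes no error at all. Its phrase about findings during EUS resembles the EUS exclusions in section IV.B. Consent precedes EUS, randomisation follows it, and the sample-size text speaks of enrolment, not randomisation. On that reading about 204 patients consent, about 152 are randomised and sampled, and intention to treat applies to those 152. This is coherent and cannot be ruled out, so it would be wrong to assert that the plan treats failures after randomisation as attrition. What stands is that the text does not choose between the readings. Screen failures are already a separate item in the same list, and on the consented reading a per-group figure is the wrong unit.

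Failures may also be rare: the series had none in 27. That limits the likely size. It does not settle it, because 0/27 has an exact 95% upper limit of 1 − 0.025^(1/27) = 12.8%.

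The series yield of 24/27 is already out of all cases attempted, so planning rates might already include failures. The plan gives no rates, so this cannot be checked.

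The allowance for loss to follow-up is legitimate, because safety is also primary and is collected to day 30. It bears little on efficacy, which comes from the procedure specimens.

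A reader might infer from the wording about patients who actually get FNA/MFB that a treated-only analysis is planned. The documents do not support that; intention to treat is stated outright.

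**Conclusion.** The point holds as an inconsistency that should be fixed, not as proof of an underpowered trial. The plan sizes for treated patients, analyses randomised ones, and defines success so that one arm cannot achieve it.

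The effect on power depends on three things the plan leaves open: how many are randomised, the technical failure rate after randomisation, and the scoring rule. At 63% v 83% with 5% to 10% failing in both arms, power is 72.5% to 65.4% with 76 randomised and 84.5% to 77.7% with 102. All of these rest on assumed rates, alpha and test.

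Two stronger readings are tempting and should not be drawn:
- **That extra enrolment is useless.** It cannot restore the difference, but it can restore power, and at 102 randomised with 5% failing in both arms it does.
- **That power collapses to about 44%.** At 102 per arm and 10% failing, this arises only if failures fall in the MFB arm alone and all are scored as non-success, including those with a diagnosis from cyst fluid (0.83 × 0.9 = 74.7% v 63%, power 43.9%). That sets MFB-only scoring in one arm against fluid-based scoring in the other, which no section states. It shows why the scoring rule must be written down; it does not estimate the trial's power.

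**What to change.** 1. Define one primary efficacy endpoint, diagnostic yield, scored the same way in both arms from all specimens taken (cytology, CEA and any MFB histology). Report MFB technical success separately, in the MFB arm.
2. Analyse all randomised patients as allocated. Count a technical failure after randomisation as a non-success unless the common endpoint is still met. Give the treated-only result as a sensitivity analysis.
3. State whether 102 per group is consented or randomised. Split the 25% into losses before randomisation, handled by consenting more patients and reported outside the per-arm figure, and missing outcomes after it.
4. Build technical failures after randomisation into the assumed success rates. Restate power at the number actually planned to be randomised, with alpha, test, rates in each arm and the missing-outcome rate. Accept a less favourable figure rather than enrolling more.
5. Minor: replace the 25%-more wording with a 25% loss, 76/0.75 = 102, or restate it after the split.

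The cost is one endpoint definition, some rewording and a recomputed power statement, all settled before outcomes are seen. The 102 should not simply be declared the number randomised. If it is the number consented, that would raise the number randomised from about 76 to 102 per arm and, at the plan's own loss rate, need 102/0.75 = 136 consented per group.
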